### 12. STUDY ADMINISTRATION

## 12.1. Regulatory and Ethical Considerations

#### 12.1.1. Regulatory Authority Approval

GSK will obtain approval to conduct the study from the appropriate regulatory agency in accordance with any applicable country-specific regulatory requirements prior to a site initiating the study in that country.

## 12.1.2. Ethical Conduct of the Study and Ethics Approval

This study will be conducted in accordance with "good clinical practice" (GCP) and all applicable regulatory requirements, including, where applicable, the 1996 version of the Declaration of Helsinki.

The investigator (or sponsor, where applicable) is responsible for ensuring that this protocol, the site's informed consent form, and any other information that will be presented to potential patients (e.g., advertisements or information that supports or supplements the informed consent) are reviewed and approved by the appropriate IEC/IRB. The investigator agrees to allow the IEC/IRB direct access to all relevant documents. The IEC/IRB must be constituted in accordance with all applicable regulatory requirements. GSK will provide the investigator with relevant document(s)/data that are needed for IEC/IRB review and approval of the study. Before investigational product(s) and CRFs can be shipped to the site, GSK must receive copies of the IEC/IRB approval, the approved informed consent form, and any other information that the IEC/IRB has approved for presentation to potential subjects.

If the protocol, the informed consent form, or any other information that the IEC/IRB has approved for presentation to potential subjects is amended during the study, the investigator is responsible for ensuring the IEC/IRB reviews and approves, where applicable, these amended documents. The investigator must follow all applicable regulatory requirements pertaining to the use of an amended informed consent form including obtaining IEC/IRB approval of the amended form before new subjects consent to take part in the study using this version of the form. Copies of the IEC/IRB approval of the amended informed consent form/other information and the approved amended informed consent form/other information must be forwarded to GSK promptly.

#### 12.1.3. Informed Consent

Informed consent will be obtained before the subject can participate in the study. The contents and process of obtaining informed consent will be in accordance with all applicable regulatory requirements.

# 12.1.4. Investigator Reporting Requirements

As indicated in Section 10.10, the investigator (or sponsor, where applicable) is responsible for reporting SAEs to the IEC/IRB, in accordance with all applicable regulations. Furthermore, the investigator may be required to provide periodic safety updates on the conduct of the study at his or her site and notification of study closure to the IEC/IRB. Such periodic safety updates and notifications are the responsibility of the investigator and not of GSK.

# 12.2. Study Monitoring

In accordance with applicable regulations, GCP, and GSK procedures, GSK monitors will contact the site prior to the subject enrollment to review the protocol and data collection procedures with site staff. In addition, the monitor will periodically contact the site, including conducting on-site visits. The extent, nature and frequency of on-site visits will be based on such considerations as the study objective and/or endpoints, the purpose of the study, study design complexity, and enrollment rate.

During these contacts, the monitor will:

- Check the progress of the study.
- Review study data collected.
- Conduct source document verification.
- Identify any issues and address their resolution.

This will be done in order to verify that the:

- Data are authentic, accurate, and complete.
- Safety and rights of subjects are being protected.
- Study is conducted in accordance with the currently approved protocol (and any amendments), GCP, and all applicable regulatory requirements.

The investigator agrees to allow the monitor direct access to all relevant documents and to allocate his/her time and the time of his/her staff to the monitor to discuss findings and any relevant issues.

At study closure, monitors will also conduct all activities described in Section 12.4, "Study and Site Closure."

## 12.3. Quality Assurance

To ensure compliance with GCP and all applicable regulatory requirements, GSK may conduct a quality assurance audit. Regulatory agencies may also conduct a regulatory inspection of this study. Such audits/inspections can occur at any time during or after completion of the study. If an audit or inspection occurs, the investigator and institution agree to allow the auditor/inspector direct access to all relevant documents and to allocate his/her time and the time of his/her staff to the auditor/inspector to discuss findings and any relevant issues.

# 12.4. Study and Site Closure

Upon completion of the study, the monitor will conduct the following activities in conjunction with the investigator or site staff, as appropriate:

- Return of all study data to GSK.
- Completion and return of all data queries to GSK.
- Accountability, reconciliation, and arrangements for unused investigational product(s) to be returned to GSK.
- Review of site study records for completeness.
- Shipment of PK/PD/biomarker samples to assay laboratory(ies).

In addition, GSK reserves the right to temporarily suspend or prematurely discontinue this study either at a single site or at all sites at any time for reasons including, but are not limited to, safety or ethical issues or severe non-compliance. If GSK determines such action is needed, GSK will discuss this with the Investigator (including the reasons for taking such action) at that time. When feasible, GSK will provide advance notification to the investigator of the impending action prior to it taking effect.

GSK will promptly inform all other investigators and/or institutions conducting the study if the study is suspended or terminated for safety reasons, and will also inform the regulatory authorities of the suspension or termination of the study and the reason(s) for the action. If required by applicable regulations, the investigator must inform the IEC/IRB promptly and provide the reason for the suspension or termination.

If the study is prematurely discontinued, all study data must be returned to GSK. In addition, arrangements will be made for all unused investigational product(s) in accordance with the applicable GSK procedures for the study.

Financial compensation to investigators and/or institutions will be in accordance with the agreement established between the investigator and GSK.

#### 12.5. Records Retention

Following closure of the study, the investigator must maintain all site study records in a safe and secure location. The records must be maintained to allow easy and timely retrieval, when needed (e.g., audit or inspection), and, whenever feasible, to allow any subsequent review of data in conjunction with assessment of the facility, supporting systems, and staff. Where permitted by local laws/regulations or institutional policy, some or all of these records can be maintained in a format other than hard copy (e.g., microfiche, scanned, electronic); however, caution needs to be exercised before such action is taken. The investigator must assure that all reproductions are legible and are a true and accurate copy of the original and meet accessibility and retrieval standards, including re-generating a hard copy, if required. Furthermore, the investigator must ensure there is an acceptable back-up of these reproductions and that an acceptable quality control process exists for making these reproductions.

GSK will inform the investigator of the time period for retaining these records to comply with all applicable regulatory requirements. The minimum retention time will meet the strictest standard applicable to that site for the study, as dictated by any institutional requirements or local laws or regulations, or GSK standards/procedures; otherwise, the retention period will default to 15 years.

The investigator must notify GSK of any changes in the archival arrangements, including, but not limited to, the following: archival at an off-site facility, transfer of ownership of the records in the event the investigator leaves the site.

# 12.6. Provision of Study Results and Information to Investigators

When a clinical study report is completed, GSK will provide the major findings of the study to the investigator.

In addition, details of the study treatment assignment will be provided to the investigator to enable him/her to review the data to determine the outcome of the study for his/her subject.

#### 12.7. Information Disclosure and Inventions

#### **Ownership**

All information provided by GSK and all data and information generated by the site as parts of the study (other than a subject's medical records) are the sole property of GSK.

All rights, title, and interests in any inventions, know-how or other intellectual or industrial property rights which are conceived or reduced to practice by site staff during the course of or as a result of the study are the sole property of GSK, and are hereby assigned to GSK.

If a written contract for the conduct of the study which includes ownership provisions inconsistent with this statement is executed between GSK and the study site, that contract's ownership provisions shall apply rather than this statement.

#### Confidentiality

All information provided by GSK and all data and information generated by the site as part of the study (other than a subject's medical records) will be kept confidential by the investigator and other site staff. This information and data will not be used by the investigator or other site personnel for any purpose other than conducting the study. These restrictions do not apply to: (1) information which becomes publicly available through no fault of the investigator or site staff; (2) information which it is necessary to disclose in confidence to an IEC or IRB solely for the evaluation of the study; (3) information which it is necessary to disclose in order to provide appropriate medical care to a study subject; or (4) study results which may be published as described in the next paragraph. If a written contract for the conduct of the study which includes confidentiality provisions inconsistent with this statement is executed, that contract's confidentiality provisions shall apply rather than this statement.

#### **Publication**

For multicenter studies, the first publication or disclosure of study results shall be a complete, joint multicenter publication or disclosure coordinated by GSK. Thereafter, any secondary publications will reference the original publication(s).

Prior to submitting for publication, presentation, use for instructional purposes, or otherwise disclosing the study results generated by the site (collectively, a "Publication"), the investigator shall provide GSK with a copy of the proposed Publication and allow GSK a period of at least thirty (30) days [or, for abstracts, at least five (5) working days] to review the proposed Publication. Proposed Publications shall not include either GSK confidential information other than the study results or personal data on any subject, such as name or initials.

At GSK's request, the submission or other disclosure of a proposed Publication will be delayed a sufficient time to allow GSK to seek patent or similar protection of any inventions, know-how or other intellectual or industrial property rights disclosed in the proposed Publication.

If a written contract for the conduct of the study, which includes publication provisions inconsistent with this statement is executed, that contract's publication provisions shall apply rather than this statement.

This includes the results of the pharmacogenetics assessments included in the study and all samples collected for those assessments.

## 12.8. Data Management

Subject data are collected by the investigator or designee using the Case Report Form (CRF) defined by GSK. Subject data necessary for analysis and reporting will be entered/transmitted into a validated database or data system. Clinical data management will be performed in accordance with applicable GSK standards and data cleaning procedures. Database freeze will occur when data management quality control procedures are completed. Original CRFs will be retained by GSK, while the investigator will retain a copy.

#### **Pharmacogenetic Data Management**

Data from the case report forms and PGx research using the coded sample will be stored electronically. International regulations for information on computers and relevant laws on processing personal information will be followed.

#### **Data Security**

Access to the data will be strictly controlled.

# 12.9. Confidentiality of a Subject's Pharmacogenetic Data

GSK advises that participation in this PGx research, withdrawal from this research, sample destruction, and/or PGx results should not be documented in the subject's medical records. Storage of information regarding the PGx research with source documents for the study is permissible if stored in the investigator study files.

Coded PGx samples and results will be associated with the subject's study specific number in computer databases. Coded PGx research results may be submitted to regulatory agencies as part of an investigational product submission and/or included in a research publication.

Individual genotype results will only be shared with a subject through the investigator if the subject requests to see their results and it is a requirement of a governmental agency or other legal authority that GSK make these results available. GSK will not release individual PGx results to anyone else (e.g., family members, primary care physicians, insurers, or employers) under any circumstance, unless required by law.

## 14.1. Appendix 1: Time and Events Table

| Study Assessments                         | Pre-Study a | Day 1
(pre-dose) | Day 10 Until
Resection | Post Study b |
|---|------------------------|---------------------|---------------------------|-------------------------|
| Informed Consent                          | Χ                      |                     |                           |                         |
| Physical Exam                             | Χ                      |                     | Х                         | Х                       |
| Medical and Medication History            | Χ                      |                     |                           |                         |
| Vital Signs                               | Χ                      | Χ                   | Х                         | Х                       |
| Clinical Labs c                | Χ                      |                     | Х                         | Х                       |
| 12-lead ECG                               | Χ                      |                     |                           |                         |
| MUGA or ECHOd                             | Χ                      |                     |                           |                         |
| AE Monitoring and Concomitant Medications | Continuous             |                     |                           |                         |
| Dosinge                                   |                        | Х                   |                           |                         |
| Tumor Biopsy / Resection f     | Χ                      |                     | Х                         |                         |
| Pharmacokinetic Sampling      |                        | Χ                   | Х                         |                         |
| Pharmacodynamic Sampling h     |                        | Χ                   | Х                         | Х                       |
| Pharmacogenetic Sampling i     |                        | Χ                   |                           |                         |

- a. All pre-study screening assessments should be scheduled within two weeks of the first dose of study drug. Screening assessments completed within 72 hours of first dose of study drug can be used as Day 1 assessments. Local lab ErbB2 results must be available prior to dosing on Day 1.
- b. The follow-up visit should occur 7-28 days after the last dose of study medication or prior to initiating adjuvant therapy.
- c. Refer to Appendix 2 for complete list of required clinical labs. Pregnancy testing is required for all women of child-bearing potential.
- d. LVEF must be  $\geq$ 50% by MUGA or ECHO to be eligible for enrollment in the study.
- e. Study drug will be dosed daily from Day 1 until the day prior to the scheduled resection.
- f. The archived tumor biopsy which is equivalent to the pre-dose tumor biopsy must be obtained prior to initiating study treatment. The post-treatment tumor resection must coincide with the previous day's lapatinib dose trough concentration and must be collected within 24 hours of last lapatinib dose.
- g. Refer to Section 6.6 for pharmacokinetic sampling schedule.
- h. Refer to Section 6.7 for pharmacodynamic sampling schedule.
- i. Refer to Section 6.8 for pharmacogenetic sampling schedule.

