# **Study Assessments and Procedures**

After obtaining informed consent, screening assessments will be completed to determine the patient's eligibility for enrollment. Screening assessments must be completed within 14 days prior to the first dose of investigational product. Screening assessments performed within 72 hours of the first treatment period may also be used as Day 1 assessments. The archived tumor biopsy obtained for diagnosis of this incidence of breast cancer must be available and shipped to a GSK Central lab for biomarker studies. Patients will receive study medication for a minimum of 9 days and continue treatment until scheduled surgical resection of the tumor (subjects must continue lapatinib treatment so that no more than 24 hours have elapsed between last dose and surgical resection). Surgical resection will coincide with the lapatinib trough concentration. The resected tumor tissue is required for biomarker and lapatinib intratumoral concentration analyses. A 2mL blood sample will be obtained at the time of tumor resection to examine steady state, trough plasma lapatinib concentrations. Safety (AEs, clinical laboratory values) will be assessed throughout the study.

Blood samples (2 x 5 ml tubes) will be obtained on Day 1, on the same day as the tumor resection and at the post-treatment safety visit to evaluate changes in circulating/secreted proteins (proteomic analysis) and biomarkers that may correlate with biological response at the tumor site and therefore provide an easily obtainable surrogate marker for determining therapeutic benefit of lapatinib.

A complete list of required study procedures is included in Section 14.1, Appendix 1.

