# 3.2. Secondary

- Evaluation of adverse events (AEs) and changes in laboratory values from pre-dose and post-dose values.
- Examination of plasma and intratumoral lapatinib steady state trough concentrations.
- Assessment of peripheral blood to examine the proteomic profile in response to lapatinib.

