### 4. STUDY DESIGN

This will be a single arm, open-label phase I study. Patients will receive 1500mg of lapatinib administered daily for a minimum of 9 days and continue treatment until surgical resection (≤24 hours).

Prior to entering the study, the documented ErbB2 status will be required for each patient. Only patients with treatment-naïve, ErbB2 positive, as defined by either overexpression of ErbB2 (3+) by semi-quantitative IHC or amplification of the ErbB2 gene by fluorescence in situ hybridization (FISH), breast tumors measuring 1 cm or greater will be eligible for the study. For eligible patients, archived tumor tissue obtained at diagnosis will represent the pre-treatment biopsy and be required for entry into the study. The pre-treatment biopsy tissue will be examined using technologies for measuring biomarkers involved in regulating tumor cell proliferation and survival (e.g., ErbB2, ERK1/2, AKT, and other downstream pathways regulated by ErbB receptor signaling). Patients will receive treatment with lapatinib for a minimum of 9 days and continue treatment until 24 hours prior to surgical resection. Patients will have their post-treatment surgical resection performed within 24 hours of last lapatinib dose. Tumor tissue obtained at resection will be examined for biomarkers as described above and compared with the results from the pre-treatment biopsy. In addition, tumor obtained at the time of resection will be examined for steady state, trough concentrations of lapatinib.

Detailed instructions on processing and shipping archived and resected tissue are included in the SRM.

Safety (AEs, clinical laboratory values) will be assessed throughout the study.

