# 6.3. On Study Assessments

On Day 1 and on the day prior to surgical resection patients will have safety, pharmacokinetic and pharmacodynamic assessments performed. The following procedures will be completed and time and date of each assessment will be documented in the source records and the CRF.

- Full physical examination, including vital signs (blood pressure and heart rate) to occur at Day 1 (if greater than 14 days since screening physical exam) and prior to scheduled surgical resection.
- Clinical Chemistry on Day 1 (if greater than 14 days since screening chemistries) and prior to scheduled surgical resection.
- Hematology on Day 1 (if greater than 14 days since screening hematology) and prior to scheduled surgical resection.

- A blood sample for pharmacokinetic analysis will be collected pre-dose on Day 1 and at the time of surgical resection. Refer to Section 6.6 for sampling schedule.
- Pharmacodynamic sampling (1 x 5 mL tubes of whole blood) on Day 1 and the on the day prior to scheduled resection. Refer to Section 6.7 for sampling schedule.
- Pharmacogenetic sampling (1 x 10 mL tube of whole blood) on Day 1 or at any time during the conduct of the study. Refer to Section 6.8 for sampling schedule.
- Assessment of study medication compliance when study medication bottle is returned prior to surgical resection.
- Assessment of adverse events continuously.
- Tumor surgical resection (≥Day 10).

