# 6.7. Pharmacodynamics

Blood samples (2 x 5 mL tubes) will be obtained pre-treatment (Day 1) and on the day prior to surgical resection to evaluate changes in circulating/secreted proteins (proteomic analysis) that may correlate with biological response at the tumor site and therefore provide an easily obtainable surrogate marker for determining therapeutic benefit of lapatinib. An additional 5 mL of blood will be obtained at the Post Study Visit to examine the changes in circulating/secreted proteins identified from the pharmacodynamic analyses.

Blood sample preparation and shipping details are contained in the Study Reference Manual.

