#### 7.3. Dose Rationale

The dose of lapatinib to be tested in this study is 1500 mg QD and was selected based upon the following criteria:

- Cell-based assays demonstrate that the lapatinib concentration required to inhibit the proliferation of either ErbB1 or ErbB2 over-expressing tumor cell lines by 90% (IC90) ranged from 520ng/mL to 1313ng/mL, depending upon the cell line. These concentrations were associated with 90% inhibition of tumor cell proliferation and comparable inhibition of ErbB1 or ErbB2 receptor tyrosine phosphorylation.
- In the initial Phase I patient study (EGF10003), lapatinib doses of 1200 mg and 1600 mg QD were well tolerated with only Grade 1/2 diarrhea and skin rash reported.
- Initial biopsies of skin, which expresses ErbB1 in the epidermis, show that doses below 1200 mg QD inhibit ErbB tyrosine autophosphorylation, indicating that 1500 mg QD is within in the biologically active dose range.
- Preliminary analysis of EGF10004 indicates that doses of 1200 mg QD produced biological activity against growth and survival pathways in tumor biopsies. Data

showed a plateau of effects on biomarkers (pErbB1, pErbB2, pAKT, and pERK) between doses 1200 mg and 1500 mg daily. No maximum tolerated dose was reached at the maximum dose given (1800 mg/day). Therefore, to ensure that patients received the optimum effect from lapatinib, the dose of lapatinib was increased from 1250 to 1500 mg/day, with the expectation that this change was unlikely to affect the safety profile.

• Pharmacokinetic data in patients receiving lapatinib doses up to 1800 mg QD indicate that QD dosing results in 1.5- to 2-fold accumulation and 3-fold fluctuation between peak and trough plasma concentrations at steady state. Based on these data, 1500 mg QD is likely to produce a steady-state plasma concentration profile with peaks that are above, and troughs that are below these *in vitro* IC90. Although steady-state trough concentrations at this dose may not exceed these *in vitro* IC90, data from animal xenografts indicate that intra-tumoral concentration exceeds and lags behind plasma concentration. Therefore, declining plasma concentrations in patients may not preclude continuous exposure in tumors with QD dosing.

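### Samples summarised as steady-state trough are not assured to be trough: the only timing limit in hours is an upper one of 24 h, and the planned analysis uses no hours since dose

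*Supplement*

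**What the plan says.** Section 3.2 names the endpoint: "Examination of plasma and intratumoral lapatinib steady state trough concentrations". The timing rules that should deliver it are spread over several places.

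- **Appendix 1, footnote f:** the resection "must coincide with the previous day's lapatinib dose trough concentration and must be collected within 24 hours of last lapatinib dose". Footnote e puts the last dose on the day before resection.
- **Protocol Summary, Study Assessments and Procedures:** resection is to coincide with trough (no hours given), with no more than 24 h since the last dose.
- **Section 4:** "Patients will receive treatment with lapatinib for a minimum of 9 days and continue treatment until 24 hours prior to surgical resection", and in the next sentence "Patients will have their post-treatment surgical resection performed within 24 hours of last lapatinib dose". The section's opening also has treatment running up to surgery, with a 24 h maximum in brackets.
- **Section 5.1:** a patient is evaluable only if the interval is within 24 h. There is no trough clause.
- **Section 6.7.1:** if surgery cannot take place within 24 h, the medical monitor is to be contacted.
- **Section 7.2:** doses are taken at about the same time each day; morning or evening is not specified.

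On analysis, Section 11.3 admits any patient with a valid concentration to the pharmacokinetic population. Section 11.4.3 ties each measurement to its treatment day. Section 11.6.1 summarises plasma and tumour concentrations in tables and graphs. Section 6.6 records sample times to the minute, and the diary in Section 7.8 records daily dosing times.

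The proteomic blood sample is placed differently in three sections. The Protocol Summary takes two tubes "on the same day as the tumor resection and at the post-treatment safety visit". Section 6.7 says "Blood samples (2 x 5 mL tubes) will be obtained pre-treatment (Day 1) and on the day prior to surgical resection". Section 6.3 says "Pharmacodynamic sampling (1 x 5 mL tubes of whole blood) on Day 1 and the on the day prior to scheduled resection".

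**The concern.** Under once-daily dosing the trough falls at about 24 h. A rule with a maximum of 24 h and no minimum in hours does not define a trough sample. With the dosing hour left free, an evening dose on the day before a daytime operation satisfies footnote e and Section 5.1, although the sample comes from the middle of the dosing interval. A resection slightly past 24 h is closer to trough but fails Section 5.1. For a patient who doses in the morning, footnote e and the 24 h limit together leave no room for an operation later in the day than her usual dosing time.

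The concentration summary could therefore mix samples from different points of the interval under one label, with every departure inside the permitted window on the high side for plasma. Section 7.3 discusses steady-state troughs against in vitro IC90 values of 520 to 1313 ng/mL, a span of 1313/520 = 2.5-fold. A timing effect of similar size would blur that comparison. The proteomic blood is meant to be related to response in the tumour, so it also matters whether it is drawn before or after the last dose.

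**Working it through.** **Inputs**

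- Plasma fluctuation (Section 7.3): "QD dosing results in 1.5- to 2-fold accumulation and 3-fold fluctuation between peak and trough plasma concentrations at steady state".
- Time of peak, 3 to 4 h (Section 1.4, healthy volunteers at low doses).
- Half-life, 9 h on Day 8 (Section 1.4, healthy volunteers, 25 to 175 mg), used for sensitivity.
- Assumptions: log-linear decline from peak to 24 h, and an interval of 8 to 14 h for an evening dose followed by daytime surgery. The protocol gives neither.

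**Consistency of the plan's own figure.** The 3-fold fluctuation is an observed value, so there is no design formula to reproduce. In a one-compartment model with instant absorption, peak/trough = 1/(1 − 1/R), where R is the accumulation ratio. R = 1.5 gives 3.0 and R = 2 gives 2.0. The stated 3-fold agrees with the lower end of the stated accumulation.

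**Plasma relative to the 24 h value.** With a 3-fold ratio and peak at time p, C(t)/C(24) = 3^((24 − t)/(24 − p)). With a 9 h half-life, C(t)/C(24) = 2^((24 − t)/9).

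For p = 4 h:

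- t = 8 h: 3^(16/20) = 2.41
- t = 14 h: 3^(10/20) = 1.73
- t = 25 h: 3^(−1/20) = 0.95

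| Hours since dose | Peak at 4 h | Peak at 3 h | 9 h half-life |
|---|---|---|---|
| 8 | 2.41 | 2.31 | 3.43 |
| 10 | 2.16 | 2.08 | 2.94 |
| 12 | 1.93 | 1.87 | 2.52 |
| 14 | 1.73 | 1.69 | 2.16 |
| 20 | 1.25 | 1.23 | 1.36 |
| 24 | 1.00 | 1.00 | 1.00 |
| 25 | 0.95 | 0.95 | 0.93 |
| 27 | 0.85 | 0.85 | 0.79 |

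At 24.5 h the first column gives 3^(−0.5/20) = 0.97.

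**Effect on a summary.** The documents give no distribution of dose-to-resection times. If times were uniform (an assumption), the geometric mean equals the ratio at the midpoint of the window:

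- 8 to 24 h: 3^(8/20) = 1.55, or 55% above trough.
- 12 to 24 h: 3^(6/20) = 1.39, or 39% above.
- A window centred on 24 h, illustrated as 21 to 27 h: 1.00, with single values from 0.85 to 1.18.

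The last line only shows what a two-sided window does to the summary. It does not propose a surgical interval.

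**Timing wording.** In Section 4, stopping at 24 h before surgery and operating within 24 h of the last dose hold together only at exactly 24 h.

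**The case against.** The strongest reply is that the protocol does require trough. Footnote f sets two joint conditions, the Protocol Summary repeats the trough requirement, and footnote e puts the last dose on the previous day. A reader might infer that a same-day sample near peak qualifies. Read together, these passages rule that out, so the arguable case is the evening dose before daytime surgery.

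A reader might also infer that tumour pairs past 24 h are thrown away. Section 11.3 sets no 24 h criterion for the pharmacokinetic or pharmacodynamic population, and Section 9.1 sets none for completion. Such a patient fails only the evaluable count in Section 5.1, which drives replacement under Section 11.4.1. The medical monitor is involved under Section 6.7.1, and Section 5 lets the monitor approve deviations.

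Nor do the documents show that the endpoint is mislabelled or biased upwards as a fact: samples near 24 h are troughs, and the spread of actual times is unknown. The ratios are for plasma. Section 7.3 says tumour concentration lags behind plasma and gives no rate, so they do not carry over to tumour or to its markers.

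Section 11.4 leaves analysis details to a Reporting and Analysis Plan that is not shown, and the study is exploratory. That covers the absence of a time covariate, but not the sampling rule, the evaluability rule or the conflicting wording, which sit in the protocol. The Summary and Section 1.5 suggest that Section 4 means no more than 24 h. That helps interpretation but still leaves no lower limit.

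**Conclusion.** The point holds in this form: the protocol does not assure that samples summarised as steady-state trough are trough. The trough requirement has no limits in hours beyond the 24 h maximum, Section 5.1 omits the trough clause, the dosing hour is free, and the stated analysis does not use hours since dose.

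For plasma at an assumed 8 to 14 h, the excess is about 1.7 to 2.4 times the 24 h value, and about 2.2 to 3.4 times with the 9 h half-life. A sample at 24.5 to 25 h is about 3 to 5% below the 24 h value (7% at 25 h with the 9 h half-life), yet the resection fails Section 5.1. These sizes rest on log-linear decline and on a time to peak from healthy volunteers at low doses. The tumour effect cannot be sized.

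A reader might go further and say that the 24 h limit itself is wrong. That is a clinical judgement about the interval before surgery, which the documents do not settle. They show only that the passages need reconciling. The differing day and tube count for the proteomic blood is a separate, smaller inconsistency. No sample size or hypothesis test depends on any of this, but what the concentration endpoint reports does.

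**What to change.** 1. Reconcile the Protocol Summary, Sections 4, 5.1 and 6.7.1, and footnotes e and f of Appendix 1 on the interval from last dose to resection. The clinical team decides the interval.
2. In Section 11.6.1, derive actual hours since last dose from the dosing diary (Section 7.8) and the recorded sample time (Section 6.6). Label as trough only samples in a pre-stated two-sided window around the end of the dosing interval, and report the others by time since dose.
3. State one collection day and one tube count for the proteomic blood in the Protocol Summary and Sections 6.3 and 6.7.
4. Optionally, add hours since dose as a covariate in a sensitivity analysis under Section 11.6.2.

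The cost is wording and one derived variable, since the times are already collected. The small downside is that fewer samples will carry the trough label.
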